## **8 RISK AND RISK MITIGATION**

**Title:** The Effect of Riboflavin on Moderate to Severe Plaque Type Psoriasis  
**Principal Investigator:** [name]

The risks to subjects in this study are minimal, as riboflavin is a common over-the-counter supplement and the dose in this study has been well tolerated in previous studies (see Background Information). Side effects of diarrhea and polyuria have been reported, but these resolved promptly with discontinuation of riboflavin. There have been no reported deaths. Riboflavin toxicity is unlikely and also reversed promptly by discontinuation of the vitamin.

At study visits and the close-out telephone call, all subjects will be screened for adverse events. Any reported events will be recorded on a standardized form, similar to the example included in [Appendix E – Adverse Events LOG](#). Basic labs will be drawn throughout the study, CBC and CMP, to monitor for potential toxicity to subjects' bone marrow, liver and kidneys. Pregnancy tests will be administered at each office visit to women of childbearing potential. As this dose of riboflavin has not been studied in pregnant women, any woman who becomes pregnant during the study will be discontinued.

Serious adverse events will be reported according to the UM IRB protocol in an expedited manner. These events include any untoward medical occurrence that results in: death, life threatening illness, hospitalization, persistent disability/incapacity, pregnancy, congenital anomaly/birth defect, an important medical event as deemed by the study investigators. Study investigators and staff will work together in this reporting.

## **9 DRUG ACCOUNTABILITY**

Study administrators, [name] and [name], will communicate with UMHS Pharmacy and coordinate the delivery of investigational medications. All investigational medications will be stored and dispensed to study administrators by the UMHS Research Pharmacy (UH B2D301), per protocol. These administrators will then hand subjects the investigational medication. At weeks 12 and 28, the study administrators will receive any excess investigational medication and record the number of returned capsules in the subjects file.

## **10 MONITORING PLAN**

A risk-based approach to monitoring will be used for this study. The study has been assigned a risk level of "minor increase over minimal risk" with the University of Michigan Institutional Review Board (IRBMED). The study drug being used has a Generally Recognized as Safe (GRAS) designation from FDA and the Select Committee on GRAS (SCOGS) concluded that there is no hazard to the public when it is used at levels currently recommended by the FDA. This is a non-complex study that involves otherwise healthy subjects who are to be seen in an established and experienced research environment, with no electronic data capture using relatively safe study drug. For these reasons, the following monitoring plan will be implemented.

An onsite, independent, trained and experienced internal monitor will be assigned to monitor the progress of the study. The monitor will use existing standard departmental standards and guidelines in conducting the study review. The frequency of the review will be dependent on study activity, but will occur at least yearly. The first review will take place no more than 2 months from the enrollment of the first subject.

**Title:** The Effect of Riboflavin on Moderate to Severe Plaque Type Psoriasis  
**Principal Investigator:** [name]

Processes/documentation to be reviewed by the monitor include:

- Communication between site staff IRBMED and subjects
- Verification of informed consent
- Adherence to protocol eligibility criteria
- Adherence to current documented protocol procedures
- Source documentation accuracy and completeness
- Procedures for documenting appropriate accountability and administration of the study drug
- Review adverse event reporting

Monitor will provide written results of the review including enrollment status, a description of any noncompliance or data irregularities, and any required corrective actions for significant issues found. Monitor will also confirm corrective actions were implemented and that reportable occurrences were reported to IRBMED. These reports will be submitted to IRBMED at the scheduled continuation review.

## **11 STATISTICAL METHODS**

A block randomization schedule will be created and all subjects randomly assigned to a sequence of treatment and dispensed study product. Assuming a large effect size and a conservative amount of correlation between the measurements, a sample size of 22 subjects in each sequence yields a statistical power of 80%.

All clinical and laboratory assessments will be descriptively summarized at each visit (weeks 0, 2, 12, 16, 18, and 28) for the modified intent-to-treat population. Continuous variables will be summarized with standard descriptive statistics including mean, standard deviation and range. Categorical variables will be summarized by frequency and percentage (N, %).

Differences within each sequence of treatment from baseline to endpoint will be assessed using parametric general linear models such as the paired t-test. The two sequences will also be compared with respect to dichotomized improvement from baseline to the 12-week visit for key clinical endpoints using the McNemar test. Assuming no carryover effects due to the four-week washout period, all data will be pooled and used to estimate the treatment effect. An analysis testing the assumption of equal carryover effects will be performed. Wilcoxon signed rank test will be used to compare ordinal or nominal assessments. Parametric t-tests will be used to determine if continuous laboratory assessments are significantly different between the treatment groups.

**Title:** The Effect of Riboflavin on Moderate to Severe Plaque Type Psoriasis  
**Principal Investigator:** [name]

An overall alpha-level of 0.05 will be used to determine statistical significance and all statistical tests will be two-sided. All data will be analyzed using SAS (SAS Institute, Inc., Version 9.3) software.

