### 3 OBJECTIVES

#### 3.1 Primary endpoint

The number of subjects that achieve a 50 percent or greater reduction in their PASI with intervention as compared to placebo.

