### 4 STUDY DESIGN

A 28-week, double-blind, placebo-controlled, prospective study with cross-over of both the riboflavin and placebo groups at the 12-week time mark.

Patients will take either 400 mg of riboflavin (“B2-400”) or a placebo by mouth once a day for 12 weeks. There will be a four week wash-out period at week 12 as the groups cross-over.

We propose using a 400 mg daily dose in this clinical trial as there is the most evidence in previous human studies for a clinical effect with this dose. While data suggesting equivalent activity of riboflavin at a lower dose is intriguing, we feel it is premature to choose a lower dose based off the findings in one trial that was stopped prematurely.

Up to 50 subjects will be enrolled. Six skin biopsies will be performed to measure metabolomics profiles, and there will be five blood draws to measure serologic markers.

**Title:** The Effect of Riboflavin on Moderate to Severe Plaque Type Psoriasis  
**Principal Investigator:** [name]

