## **6.3 Return Visits - Weeks 2, 6, 12, 16, 18, 22 and 28**

1. Measure vital signs.
2. Review medical history, adverse events and concomitant medications.
3. Skin Exam: Complete PASI, PGA, DLQI, and pruritus assessment using visual analog scale (VAS).
4. For females of childbearing potential, obtain a negative urine pregnancy test.
5. Photographs will be taken of significant lesions on weeks 0, 12, 16, and 28.

**Title:** The Effect of Riboflavin on Moderate to Severe Plaque Type Psoriasis

**Principal Investigator:** [name]

6. One PP and one PN 6 mm punch biopsy will be performed at week 12. These will be performed as described above. This will be a total of 6 biopsies throughout the study.
7. 20 mL of blood will be drawn for measuring plasma levels of riboflavin and FAD on weeks 2, 12, 18 and 28.
8. 9 mL of blood will be drawn for measuring CBC, CMP on weeks 12 and 28.
9. At week 12 all residual medication will be collected and counted in preparation for patients to cross-over. There will be a four week wash-out period between weeks 12 and 16. At week 16 new medication will be provided and the data from this visit will be used as our new baseline for the second part of the study.
10. At week 28, all residual medication will be collected and counted.

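### McNemar's test is assigned to the week-12 comparison of the two randomised sequences, which are independent groups with no pairs

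*Combined protocol and SAP*

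**What the plan says.** Section 11 (Statistical Methods) has "all subjects randomly assigned to a sequence of treatment and dispensed study product". It later says that the treatment "sequences will also be compared with respect to dichotomized improvement from baseline to the 12-week visit for key clinical endpoints using the McNemar test".

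Section 4 (Study Design) describes "cross-over of both the riboflavin and placebo groups at the 12-week time mark". Section 6.3 agrees: "At week 12 all residual medication will be collected and counted in preparation for patients to cross-over". Washout then runs to week 16, whose data become the baseline for the second part, ending at week 28.

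Section 3.1 gives the primary endpoint as "The number of subjects that achieve a 50 percent or greater reduction in their PASI with intervention as compared to placebo". For other non-continuous outcomes Section 11 says only that the "Wilcoxon signed rank test will be used to compare ordinal or nominal assessments". It names no chi-square test, Fisher's exact test or logistic regression. The sample-size sentence begins "Assuming a large effect size and a conservative amount of correlation between the measurements" and claims 80% power with 22 subjects per sequence.

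**The concern.** McNemar's test compares two binary results recorded on the same person, or on individually matched people. Baseline to week 12 is the first treatment period only, so every subject contributes one result on one product. The comparison between sequences is then an ordinary two-group comparison, and the named test has nothing to work on.

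The slip matters because no other test is clearly assigned to a responder endpoint. PASI 50, the higher PASI thresholds and the 0/1 scores for PGA, pruritus and DLQI are all binary. The signed rank test, the only other candidate, is also paired. PASI 50 would naturally fall among the key clinical endpoints in the McNemar sentence, although the plan does not list it there or call this comparison primary. An analyst would have to choose a substitute, possibly with the data in view.

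**Working it through.** **Structure of the comparison.** Unit: the subject, randomised to one sequence (Section 11). Time: baseline to week 12, before cross-over (Sections 4 and 6.3). Results per subject in that window: one. Matching: none described; block randomisation balances numbers but does not pair individuals. The groups are independent.

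**The plan's own figure.** The 80% power cannot be reproduced, because the effect size and correlation are given only in words. If "large" is taken as d = 0.8, a paired t-test with standardised difference d/√(2(1−ρ)) and n = 22 has power 72% at ρ = 0, 81% at ρ = 0.2 and 95% at ρ = 0.5. A parallel comparison of 22 versus 22 has 74%. The finding does not depend on this figure.

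**Inputs for the consequences.** 22 per sequence and two-sided 0.05 are from Section 11. The plan gives no PASI 50 planning rates, so the response rates below are assumptions. With discordant counts b and c, asymptotic McNemar refers (b−c)²/(b+c) to χ² on 1 df; exact McNemar is p = 2·P(X ≤ min(b,c)) with X ~ Bin(b+c, ½). Rejection rates come from enumerating all pairs of responder counts and rejecting when p ≤ 0.05.

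**Route 1: unrelated subjects are paired across sequences.** With 11/22 and 4/22 responders and k pairs in which both respond, b = 11−k and c = 4−k. Under random pairing, P(k) = C(11,k)·C(11,4−k)/C(22,4).

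| k | b, c | Probability | Exact p | Asymptotic p |
|---|---|---|---|---|
| 0 | 11, 4 | 0.045 | 0.118 | 0.071 |
| 1 | 10, 3 | 0.248 | 0.092 | 0.052 |
| 2 | 9, 2 | 0.414 | 0.065 | 0.035 |
| 3 | 8, 1 | 0.248 | 0.039 | 0.020 |
| 4 | 7, 0 | 0.045 | 0.016 | 0.008 |

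Fisher's exact test on the same data gives a single value, 0.055. The share of random pairings that reach significance is 0.248 + 0.045 = 29% with the exact test, and 0.414 + 0.248 + 0.045 = 71% with the asymptotic one. Averaged over random pairings, type I error is 0.5–4.6% at common response rates of 10–50%. Power at 60% versus 20% is 67% (exact) to 76% (asymptotic), against 69% for Fisher. The error rate is therefore controlled, but the result is arbitrary. Unequal sequence sizes would leave some subjects unpaired.

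**Route 2 (illustrative misuse): the sequence-by-response table is entered as a paired table.** With x_A and x_B responders, the off-diagonal cells are b = 22−x_A and c = x_B. Their expectations are equal when 1−p_A = p_B, so the test asks whether p_A + p_B = 1. For 4/22 versus 4/22, b = 18 and c = 4. Exact p = 2·(1 + 22 + 231 + 1540 + 7315)/2²² = 18218/4194304 = 0.004. The asymptotic statistic is 14²/22 = 8.91, p = 0.003. Fisher gives p = 1.0.

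| Equal true rate | McNemar rejects (exact to asymptotic) | Fisher rejects |
|---|---|---|
| 10% | >99% | 1.4% |
| 20% | 87–93% | 2.4% |
| 30% | 34–48% | 2.4% |
| 40% | 4–8% | 2.2% |
| 50% | 0.3–0.7% | 2.3% |

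The rates are the same whichever way the columns are ordered. At a true 60% versus 20% this misuse rejects 11–17% of the time in one column order and 0.8–2.2% in the other, against 69% for Fisher.

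**The case against.** The strongest reply is that the sentence is a slip, with sequences written for treatments. The sample-size statement assumes correlated measurements, each treatment period lasts 12 weeks, week 16 serves as a fresh baseline, and the next sentence pools all data to estimate the treatment effect. If the intention was to compare each subject's response on riboflavin with the same subject's response on placebo, McNemar is a recognised choice, though it ignores period effects. This is a plausible account of how the wording arose, but it does not remove the error. The text names the sequences and stops at the 12-week visit, and pooling is a separate step. The sentence would still have to be rewritten.

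A second reply is that the comparison may only be supportive, since the plan says the sequences will also be compared. That is possible. The weight of the point comes from the binary primary endpoint having no other clearly assigned test.

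A third reply concerns the most dramatic figures. They belong to a misuse the plan does not call for and depend strongly on the assumed rate; at 50% response, rejection falls below the nominal level. That is fair, and Route 2 should be read as an illustration, not a prediction.

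**Conclusion.** The concern holds. Under the text as written, a paired test is assigned to two independent groups, and the week-12 responder comparison cannot be run reproducibly. That conclusion rests on the design alone and needs no assumed response rates.

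The size of the consequence does depend on assumptions. Under arbitrary pairing the harm is an arbitrary p-value (0.016 to 0.118 in the 11/22 versus 4/22 example), with type I error not inflated. If the table were treated as paired, the test would answer the wrong question, with false rejection anywhere from below 1% to above 99% over common rates of 50% down to 10%. The matter should be settled before analysis, because the choice of substitute test affects which subjects, periods and power apply to the responder comparison.

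**What to change.** In Section 11:

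1. For the between-sequence comparison of dichotomized improvement at week 12, replace McNemar with an independent-groups test, for example Fisher's exact test.
2. Reserve McNemar, or a period-adjusted form such as Mainland-Gart, for each subject's response in the riboflavin period against the same subject's response in the placebo period. If that is what was meant, reword the sentence so that it refers to treatments and to the end of each period.
3. State which of the two is the primary PASI 50 analysis, tested at two-sided 0.05, and label the other supportive.

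Correcting the test costs the wording of one paragraph, with no new data, visits or patients. One caution applies to step 3: if the week-12 comparison is made primary, the stated 80% power cannot be assumed to carry over. At 22 per group, Fisher's power is 28%, 55% and 79% for assumed rates of 30%, 40% and 50% against 10% on placebo. Against 20% on placebo, it is 21%, 43% and 69% for 40%, 50% and 60%.

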## 1 SYNOPSIS

The purpose of this investigation is to determine the anti-inflammatory effect of high-dose riboflavin supplementation on chronic plaque psoriasis. Up to fifty volunteers with chronic plaque psoriasis will be recruited for a double-blind, placebo-controlled 28 week prospective study with cross-over of both the intervention and control groups at the 12 week time mark. There will be a 4 week washout period when subjects crossover. Riboflavin will be dosed 400 mg by mouth daily versus placebo. Throughout the study we will perform both clinical and laboratory assessments to measure response. Clinical assessment will include the Psoriasis-Area-and-Severity-Index (PASI), Physician Global Assessment (PGA), Dermatology -Life-Quality-Index (DLQI) and pruritus assessment will be performed at all clinical evaluations. Photographs of volunteers' skin will be taken. Skin punch biopsies of psoriasis plaques and uninvolved skin will be performed at pre-determined time points throughout the study to measure metabolomics and RNA profiling as well as histologic markers. Patients will also have regular blood draws to follow plasma measurements of riboflavin and Flavin-adenine-dinucleotide (FAD).

The primary objective is to demonstrate the superiority of riboflavin as compared to placebo at achieving a PASI 50 response (a 50% or greater improvement in PASI from baseline). Secondary objectives include, measuring the efficacy of the intervention at achieving a PGA, DLQI, or pruritus assessment score of 0/1. All statistics will be performed on a modified intent-to-treat population.

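### Section 11 gives the week-12 comparison of two independent sequences a paired test, and does not say whether that comparison or the pooled crossover analysis decides PASI 50

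*Combined protocol and SAP*

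**What the plan says.** The Synopsis sets the question: "The primary objective is to demonstrate the superiority of riboflavin as compared to placebo at achieving a PASI 50 response". Section 3.1 defines the primary endpoint as "The number of subjects that achieve a 50 percent or greater reduction in their PASI with intervention as compared to placebo". Neither gives a visit, a period or an analysis.

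Section 11 describes two analyses that could answer it. The first is worded: "sequences will also be compared with respect to dichotomized improvement from baseline to the 12-week visit for key clinical endpoints using the McNemar test". In the second: "Assuming no carryover effects due to the four-week washout period, all data will be pooled and used to estimate the treatment effect". No test or model for a binary outcome is named for the second, and neither is called primary.

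On carryover, Section 11 adds: "An analysis testing the assumption of equal carryover effects will be performed". On error control: "An overall alpha-level of 0.05 will be used to determine statistical significance", with all tests two-sided. The sample size is 22 per sequence for 80% power, with the effect described only as large and the correlation only as conservative. Section 6.3 sets the second-period baseline at week 16: "the data from this visit will be used as our new baseline for the second part of the study".

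**The concern.** McNemar's test uses only the discordant members of matched pairs. At week 12 one sequence has had riboflavin and the other placebo, and they are different, separately randomised people. There are no pairs. To run the test, someone must create a pairing, and the p-value then depends on the pairing chosen. McNemar would suit a comparison of each patient's riboflavin period with the same patient's placebo period, but that is the analysis for which no binary test is given.

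As neither analysis is designated, the one that decides PASI 50 could be settled after the results are known. The two can disagree, because they differ widely in power and only the pooled one depends on the washout being complete.

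**Working it through.** **Inputs.** From Section 11: 22 per sequence, two-sided 0.05, power 80%. From Section 4: at most 50 subjects. The documents give no PASI 50 rates, no numerical effect size and no correlation, so every rate, standardised effect and correlation below is an assumption.

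**1. The stated 80%.** It cannot be strictly reproduced. With an assumed standardised effect d = 0.8:
- Week 12 between sequences, normal approximation: Φ(0.8·√(22/2) − 1.96) = Φ(0.69) = 75.6% (73.6% with the t distribution).
- Within-subject crossover, 44 subjects, 42 df, noncentrality d·√44/√(2(1−ρ)): 95.6% at ρ = 0 and 99.2% at ρ = 0.3.

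For 80%, the week-12 comparison needs d of about 0.85 to 0.87, and the crossover about 0.61 (ρ = 0) to 0.51 (ρ = 0.3). The stated power therefore does not show which analysis the trial was sized for.

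**2. McNemar on independent groups.** Take 9/22 versus 2/22 responders. An arbitrary 1:1 pairing puts k = 0, 1 or 2 responder pairs together, leaving discordant counts (9−k, 2−k). The exact p-value is twice the binomial tail at one half:
- (9, 2): 2(1 + 11 + 55)/2¹¹ = 0.065
- (8, 1): 2(1 + 9)/2⁹ = 0.039
- (7, 0): 2/2⁷ = 0.016

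Fisher's test on the same data gives 0.034.

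**3. Power of the two analyses for PASI 50.** The within-subject test here is exact Prescott: score each patient as period-1 response minus period-2 response (−1, 0 or 1) and compare the score sums between sequences by permutation. Correlation is that of a latent normal response; no carryover.

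| Assumed response | Fisher, week 12 | Exact Prescott |
|---|---|---|
| 10% vs 40%, ρ = 0 | about 55% | about 87% |
| 10% vs 40%, ρ = 0.5 | about 55% | about 95% |
| 20-point differences (10 vs 30%, 20 vs 40%), ρ = 0 to 0.5 | 20–28% | 42–68% |

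**4. The carryover test.** No method is stated, so I tried two on a continuous outcome in SD units (noncentral t, ρ = 0 to 0.7).
- Subject totals, SE = √(2(1+ρ))·√(2/22), 42 df: power 11–15% for carryover of 0.4 SD, 29–45% for 0.8 SD.
- Week 16 adjusted for week 0, SE = √(1−ρ²)·√(2/22), 41 df: 25–44% and 74–95%.

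Modest carryover would usually be missed by either.

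**5. False-positive chance if either result could be claimed.** In large samples the two statistics have correlation √((1−ρ)/2), giving 0.083 to 0.094 for ρ = 0 to 0.7. Simulated PASI 50 under the null with asymptotic tests gives about 0.08 to 0.09 (single settings from 0.071 to 0.098). With exact tests it is 0.020 to 0.048 at 22 per sequence, and about 0.05 at 25 per sequence.

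**6. Period-2 baseline.** Assume a normal model for log-PASI change and a true difference of 30 points (10 vs 40% or 20 vs 50%). Let f be the share of riboflavin benefit left at week 16 and g the share of that left at week 28, with z_P and z_R the normal quantiles of the two response rates. Period-2 placebo response is Φ(z_P + f·g·(z_R − z_P)) from a week-0 baseline and Φ(z_P − f·(1−g)·(z_R − z_P)) from a week-16 baseline. With f = 0.5 and g from 0 to 1:
- Week-16 baseline: pooled difference 30 to 35 points; unbiased at g = 1.
- Week-0 baseline: pooled difference 23 to 30 points; unbiased at g = 0.

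**The case against.** The strongest defence is that the wording already leans toward the pooled analysis: the week-12 comparison is introduced as an addition, and the pooled one is said to estimate the treatment effect. That is fair, but a lean is not a designation, and no binary test is attached to it. Nor does Section 11 name PASI 50 in either sentence: the first speaks of key clinical endpoints, and the second could be read as continuous PASI. A dichotomised improvement in a key endpoint must include the primary one. If the pooled analysis is not of PASI 50, the primary endpoint is left with only the McNemar comparison.

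Four stronger readings are tempting, and the documents do not support them:
- **That the trial runs at nearly 10% type I error.** The plan does not say that either result suffices, though it does not rule it out. The excess depends on asymptotic tests; with exact tests the figure is about 0.05 or less.
- **That a carryover pre-test chooses the analysis.** Section 11 does not make pooling depend on it.
- **That the carryover test has no significance level.** The general two-sided 0.05 covers it. What is missing is its method and what follows from its result.
- **That the second-period baseline is undefined.** Section 6.3 sets week 16. Section 11 merely does not repeat it.

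Preferring the crossover to week 12 as primary is partly a design choice. It follows the design that the sponsor chose, but the essential point is that one analysis be named.

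**Conclusion.** Two defects stand, and no other section cures them. The McNemar test is assigned to independent groups and cannot be used as written. No analysis is named as the one that decides PASI 50, although the candidates differ by roughly 30 to 40 points of power at 10% versus 40% response. Pooling also rests on an assumption of no carryover that a non-significant test would support only weakly, since modest carryover is likely to go undetected at this size. Inflation of the false-positive rate is conditional and should not lead the argument. The pairing example is exact arithmetic on illustrative counts; the power and carryover figures rest on rates, effects and correlations that I assumed. The trial remains interpretable, but Section 11 should be corrected before unblinding.

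**What to change.** In Section 11:

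1. Replace McNemar at week 12 with a test for independent groups, for example Fisher's. Report it as a pre-specified sensitivity analysis that carryover cannot affect, with no separate claim at 0.05.
2. Name one primary analysis at two-sided 0.05: the within-subject PASI 50 comparison of riboflavin with placebo, adjusted for period (for example exact Prescott or Mainland-Gart), at weeks 12 and 28. Use the week-16 second-period baseline already set in Section 6.3, with a week-0 baseline as a sensitivity analysis.
3. State that the carryover result does not select the analysis, and report it as an estimate with a confidence interval.

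**Cost.** Wording and two sensitivity analyses. PASI is already scheduled at weeks 0, 12, 16 and 28. A positive week-12 result alone would no longer be formal success. Without carryover, this costs about 0 to 4 points of power against claiming either test in the scenarios tried: 95.3% against 95.7% at 10% versus 40% (ρ = 0.5), and about 3.5 points at 10% versus 25% (ρ = 0).

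Neither baseline is safe if benefit remains at week 16. The week-16 baseline can overstate the difference (step 6). The week-0 baseline can understate it and lose power: at 10% versus 40% and ρ = 0.5, from 95% to about 81% or 58% if second-period placebo response rises to 20% or 30%. This is why both baselines and week 12 should be reported.

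Keeping both analyses confirmatory at 0.025 each would be dearer. At d = 0.845, where 22 per sequence gives 80% for week 12, power falls to Φ(0.845·√11 − 2.241) = 71%. Restoring 80% needs 2(2.241 + 0.842)²/0.845² = 26.6, so 27 per sequence or 54 in all, above the cap of 50.

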#### **5.5.1 Inclusion Criteria**

Subjects must meet all of the following criteria for inclusion in the study:

1. 18 years of age or older

**Title:** The Effect of Riboflavin on Moderate to Severe Plaque Type Psoriasis

**Principal Investigator:** [name]

2. Good general health
3. Willingness and ability to follow the protocol
4. Signed Informed Consent Form, written and witnessed.
5. Stable moderate to severe chronic plaque psoriasis involving 5% or greater total body surface area (TBSA).
6. If subject is a woman of childbearing potential, she must have a negative pregnancy test at screening and agree to use a medically acceptable form of contraception during the screening and throughout the study.

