## **6.2 Admission/Day 0**

1. Measure vital signs.
2. Review medical history, adverse events and concomitant medications.
3. Skin Exam: Complete PASI, PGA, DLQI, and pruritus assessment using visual analog scale (VAS).
4. Photographs will be taken of significant lesions.
5. Randomize patient
6. For females of childbearing potential, obtain a negative urine pregnancy test.
7. 20 mL of blood will be drawn for measuring plasma levels of riboflavin and FAD.
8. Two psoriatic normal (PN) and two psoriatic plaque (PP) skin samples will be obtained (four total at this visit). These will be performed under local anesthesia (1% lidocaine with epinephrine) using a 6 mm skin punch to obtain skin through to subcutaneous fat. Closures will be made with 4-0 prolene sutures that should be removed in two weeks. Verbal wound care instructions will be provided.
9. Dispense medication.

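### PASI is scored at the start of each period, but section 11 names no baseline covariate for PASI 50; adjusting for both period baselines is a cheap way to gain precision, by an amount the plan's figures cannot fix

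*Combined protocol and SAP*

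**What the plan says.** Section 6.2 (Admission/Day 0) lists, before dosing, "Skin Exam: Complete PASI, PGA, DLQI, and pruritus assessment using visual analog scale (VAS"). Section 6.3 repeats these assessments at every return visit and, for the crossover, states: "At week 16 new medication will be provided and the data from this visit will be used as our new baseline". Table 1 confirms PASI at weeks 0 and 16. The primary endpoint (section 3.1) is a PASI reduction of at least half, so each period's response is judged against that period's own starting score.

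Section 11 gives McNemar's test for dichotomised 12-week improvement, paired t-tests or similar linear models within sequence, the Wilcoxon signed rank test, and t-tests for laboratory values. For the crossover as a whole it says, assuming no carryover, that "all data will be pooled and used to estimate the treatment effect". It also plans a test of equal carryover. No model is named for the pooled PASI 50 analysis. No baseline covariate appears anywhere in the section, and no reason is given for omitting one.

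On size, section 11 claims that "a sample size of 22 subjects in each sequence yields a statistical power of 80" percent. The only basis it offers for that figure is the phrase "Assuming a large effect size and a conservative amount of correlation between the measurements", with no numbers attached. Section 4 adds: "Up to 50 subjects will be enrolled".

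**The concern.** Using baseline to define response is not the same as adjusting for it. A subject who happens to score high at week 0 is more likely to halve the score by week 12 on either capsule, through regression to the mean. The same holds at week 16. Pairing does not remove this noise, because weeks 0 and 16 are separate measurements and each enters a different period's outcome. A covariate that captures the difference between the two baselines can remove part of it.

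What is at stake is precision in a small trial. The calculation needs 2 × 22 = 44 subjects and enrolment stops at 50, so there are only 6 to spare and power cannot readily be bought with more subjects. The two baselines are already being collected.

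**Working it through.** **1. The plan's own figure.** The stated 80% cannot be reproduced, because the effect size and correlation have no numbers and the figure is not tied to PASI 50. Several routes come near it or straddle it:
- Taking 0.8 for a large standardised effect (an assumption), 22 per group in a two-sample comparison gives 75.6% (normal) or 73.6% (t), and 25 per group are needed for 80%.
- The same effect in a paired comparison of 44 with zero correlation gives 95.6%.
- A paired comparison of 44 reaches 80% at a standardised within-subject difference of about 0.43.
- Response of 15% versus 55% in two independent groups also gives 22 per group.

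None of these is documented, so 80% is used below only as a starting point, with the plan's two-sided alpha of 0.05.

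**2. Formula.** Let r be the correlation, within sequence, between the within-subject difference in PASI 50 response and the difference in log PASI between the two period starts. Adjustment multiplies the residual variance by 1 − r², so

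adjusted power = Φ[(1.960 + 0.842)/√(1 − r²) − 1.960].

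| r (assumed) | √(1 − r²) | Φ argument | Power | Gain (points) |
|---|---|---|---|---|
| 0.2 | 0.980 | 0.899 | 81.6% | 1.6 |
| 0.3 | 0.954 | 0.977 | 83.6% | 3.6 |
| 0.4 | 0.917 | 1.097 | 86.4% | 6.4 |
| 0.5 | 0.866 | 1.275 | 89.9% | 9.9 |

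**3. Simulation of PASI 50 in this design.** There were 22 subjects per sequence, with log PASI at weeks 0, 12, 16 and 28, response judged from each period's own baseline, and no carryover. The within-subject response difference was regressed on sequence, with and without the baseline difference. All response rates, SDs and correlations are assumed.

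With the effect tuned to about 80% unadjusted power, placebo response of 10% or 20%, and serial correlation over 12 weeks of 0, 0.5 or 0.8:
- visit-to-visit fluctuation as the only noise: gain 7.6 to 11.9 points;
- between-subject variation in response equal to that fluctuation: 1.5 to 7.0;
- response variation at least twice the fluctuation: −1.0 to 3.3.

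The correlation r ran from 0.05 to 0.54 across these settings. A second set, at 15% versus 42% response and log-PASI SD 0.6, gave:
- +4 to +10 points with no response variation;
- +3 to +8 at response SD 0.3;
- 0 to +5 at SD 0.6;
- about 0 to +2.5 at SD 0.9.

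Type I error of the adjusted test was 4.7% to 5.6%.

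**4. Week-12 comparison alone.** At 15% versus 42%, power went from 52.6% to 58.1% with all visits correlated 0.5, and from 52.3% to 53.5% under serial correlation of 0.85. The gain is roughly 0 to 5 points.

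**5. Carryover.** Week-16 PASI is measured after period 1 treatment. In one illustrative scenario, power without and with adjustment was:
- no carryover: 94.1% and 96.5%;
- 25% of the period 1 change persisting at week 16: 95.5% and 93.9%;
- 50% persisting: 95.8% and 84.1%.

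In the 15% versus 42% runs with 50% persisting, adjusted power was 69–80% against 82–89% unadjusted, and the adjusted estimate shrank.

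**The case against.** The strongest case against is that adjustment may gain nothing here. Entry requires "Stable moderate to severe chronic plaque psoriasis involving 5% or greater total body surface area (TBSA"). Stable disease suggests high correlation between visits and little baseline noise, and if subjects differ widely in how they respond, the simulated gain is near zero or slightly negative. This stands, and it rules out any fixed lower bound on the loss. It also disposes of the argument that a body-surface floor without a PASI range makes adjustment necessary, since stable differences between subjects cancel in the within-subject contrast.

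The carryover objection also stands. Section 11 assumes no carryover but also plans to test the equal-carryover assumption, and if the assumption fails badly the adjusted analysis can do worse. Unadjusted power is not a clean benchmark in that case either, because a week-16 score still lowered by riboflavin makes response on placebo harder to reach.

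The choice of model matters too. The powers above belong to the linear regression of differences. In small runs of 700 trials each, a logistic GEE gained 7.8, 5.5 and 2.7 points where the linear model gained 9.7, 9.3 and 4.0.

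Finally, section 11 leaves the pooled model unspecified. A reader might infer that the plan commits to an unadjusted analysis; the text does not say so. What it lacks is a decision either way.

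**Conclusion.** The point holds as an efficiency improvement. Both period baselines will be available, no PASI 50 analysis is said to use them as covariates, and without carryover adjustment keeps type I error near 5% and can add power. The size is conditional: about 2, 4 and 10 points from an 80% start at r of 0.2, 0.3 and 0.5, and from about zero to about 10 points in simulation (individual settings ran from −1 to +12).

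A reader might infer that the plan definitely forfeits 4 to 10 points. The documents do not support that. The range corresponds to r of 0.3 to 0.5, or to visit noise being the only source of variation, and the plan states no response rates, SD or correlation and does not link its 80% to PASI 50. Nor does anything here show that the planned comparison is biased or invalid for want of a covariate.

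**What to change.** In section 11, specify the pooled PASI 50 analysis in advance as a within-subject comparison adjusted for period and for log PASI at the start of each period. Either form would serve:
- regression of the within-subject response difference (period 1 minus period 2) on sequence and on the week 0 minus week 16 log-PASI difference, with robust standard errors (the form simulated, and the more workable one if responders are few); or
- a logistic GEE clustered on subject, with treatment, period and period-baseline log PASI, reported as a standardised difference in response proportions so that the section 3.1 endpoint is unchanged.

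A week-0 covariate alone is not enough, because it cancels in the within-subject comparison. If the week-12 comparison is kept, week-0 log PASI can be added there for a small gain.

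State that the adjusted estimate relies on the no-carryover assumption and can lose power and shrink toward zero if carryover is substantial. Report the unadjusted pooled result as a sensitivity analysis.

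The cost is SAP wording, a few lines of SAS and one extra parameter. No new data or subjects are needed.
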